6. DATA COLLECTION

6.1. HOSPITAL DATA (ANNEX I WP5 DF1 HOSPITAL DATA)

In order to make descriptive comparisons of the groups of wards randomized to the two strategies, hospital and ward characteristics will be collected.

Data	Collected by	
	Local study personnel	Ward personnel
Hospital and ward characteristics ¹	X	
x ¹ once x ^a annually x ^m monthly x ^d daily		

6.2. WARD DATA (ANNEX II WP5 DF2 WARD DATA)

Data	Collected by	
	Local study personnel	Ward personnel
General characteristics ¹	X	
Total AHC ^m	X	
Pharmacy report ^m	X	
Number of admissions ^d	X	X
Patients on ward ^d	X	X
Patients isolated ^d (only Study Intervention Periods)	X	X
Patients isolated for ESBL-E ^d	X	X
AHC assessed by disinfection dispensers with monitoring system (patient rooms only) ^d	X	
x ¹ once x ^a annually x ^m monthly x ^d daily		

Occupancy rates will be collected daily at the same time (preferably midnight patient census).

6.3. PATIENT DATA (ANNEX III WP5 DF3 ESBL-E PATIENT)

The following data will be only obtained from patients who are ESBL-E-positive (“Cases”)

Data	Collected by	
	Local study personnel	Ward personnel
Known ESBL-E patient at admission (Yes / No) ¹	X	
Day of admission (Day of study) ¹	X	
Day of discharge (Day of study) ¹	X	
Day of finding (Day of study) ¹	X	
Reason for sampling (Screening/ Clinical/ No sample) ^d	X	
Sample: ESBL-E (Positive: E. coli; Klebsiella; other/ Negative / No data) ^d	X	
Pos. Result known (documented in patient file on the ward) (Yes / No / Known ESBL-E) ^d	X	
Contact Precautions (CI 1-4 / SP 1-4 / No data) ^d	X	
ESBL-E Infection (No / Yes ___) ^d	X	
Handrub Consumption (ml / day) ^d	X	
Antibiotic Use (Yes / No ___, if yes, type of antimicrobial substance ___) ^{d,e}	X	
x ¹ once x ^a annually x ^m monthly x ^d daily x ^e in a subset of patients		

If a patient is ESBL-E-positive for the first time during the study these data should be filled in retrospectively preferably from the day of admission onwards, but at least for the 6 days prior to the first ESBL-E result.

6.4. SURVEILLANCE CULTURES

Surveillance cultures of the rectal skin will be obtained as soon as possible after admission to the ward, at the latest within three days and once a week thereafter for patients staying longer than 7 days. Patient care nurses and/or research personnel will obtain the surveillance cultures from the patients.

Swabs of the rectal area will be obtained following a standardized procedure. Swabs will be processed in the institutional microbiology laboratory.

Rectal swabs will be plated on chromogenic media. If no characteristic colonies are present, the culture will be recorded as negative. Characteristic colonies will be confirmed with ESBL-E-disk tests and E-tests, if possible. The laboratory will report surveillance culture results back to the wards as soon as possible after final confirmation and identification. Efforts will be implemented to speed up the notification process, including weekends.

All confirmed ESBL-E isolates will be frozen in appropriate storage at -70°C. At three months intervals, the isolates will be shipped in batches to Madrid (SERMAS) for further molecular analysis.

7. MONITORING

7.1. CONTINUOUS MONITORING OF CI

The implementation of CI will be monitored once a week by local research personnel. The monitor will observe whether gloves and gowns are available for known ESBL-E-carriers, whether correct signage is placed on the patient bed and material, and if the patient is placed in a single or a shared room.

The implementation of CI will be listed on the patients' data forms (Annex III DATA FORM 3 «ESBL-E Patient»).

7.1.1. OBSERVATION OF HAND HYGIENE AND USE OF PROTECTIVE CLOTHING

Research personnel at each site will conduct direct human observations of compliance with HH and use of protective clothing. A minimum of 200 HH opportunities for each ward and intervention arm will be observed semiannually according to WHO methods ²⁸. At least 20 opportunities will be monitored for patients known to be colonized/ infected with ESBL-E-producing organisms. The use of protective clothing for CI as well as SP will also be recorded. All health care workers in the ward at the time of the observations will be eligible for monitoring. Observations will be recorded anonymously for both the patient and the HCW.

Monitoring personnel will be trained by Charité Berlin during the introductory course at the study site (see point 5.6.Training).

The results of the observations will be reported back to the wards.

In order to assess AHC from belt/pocket bottles and other disinfection dispensers beside the electronic counting devices, total AHC of the ward per year will be recorded.

7.1.2. AUTOMATIC HAND HYGIENE COUNT DEVICES

HH compliance will also be monitored by the use of ABHR dispensers with automatic hand hygiene count devices for every patient. Each hand hygiene event and the amount of disinfectant dispensed per stroke will be documented.

If the automatic count devices cannot be installed for all patient beds, if other disinfectant sources in the study sites cannot be replaced, or if a clear allocation to a specific patient bed is impossible, weekly point prevalence observations of compliance with HH are required.

7.2. MONITORING OF ANTIBIOTIC USE

The systemic antibiotic use at the ward-level will be collected monthly, in DDD per 1000 patient-days in ATC J01 classes.

8. DATA MANAGEMENT

Research Online's internet-based remote data entry system will be used to capture data for this study, including hospital, ward and patient level data.

Clinical and study personnel will collect data on paper forms, which will be stored securely at the study site. After the data have been recorded, on-site study personnel will use an internet browser to enter data into electronic case report forms (eCRFs). For completing both paper and electronic forms, guidelines will be provided to each site. All data on paper forms must be legibly recorded. Data are submitted to Research Online's secure web server and stored in the study's operational database. Authorized site personnel may log in to the system at any time, review and correct previously entered data, or put in additional data. Personnel will only be able to access information for subjects at their site.

Data will only be stored in the central database.

No study participants or HCWs will be identified by name on any study documents or electronic data submissions.

The Julius Center located at UMC Utrecht will provide data management support for this project. UMCU's programming team will create and validate datasets for statistical analysis.

9. STATISTICAL ANALYSIS

9.1. SAMPLE SIZE

20 wards in Europe will participate in this cluster-randomized, multi-center, crossover-design study.

Calculations are based upon the following assumptions:

- For this study, the average incidence of nosocomial acquisition of ESBL-E-producing *Enterobacteriaceae* determined using regular surveillance cultures is assumed to be at least 0.8 per 100 patients in Non-ICUs, a ratio of 1:1 for exposed (CI) and unexposed (SP) patients, $\alpha=0.05$, and $\beta = 0.80$. This assumption is considered to be reasonable because the incidence of MDRO colonization determined by regular surveillance cultures is substantially higher than MDRO incidence determined by cultures obtained for clinical indications only^{29, 30}.
- Because CI does have side effects for the patients and is both resource- and time-intensive and all ESBL-E-patients are identified by routine surveillance cultures, the study is powered to detect a 50% reduction in the incidence of ESBL-E-acquisition compared to the SP strategy.
- Based on these preconditions, 12,686 patients will be observed in the trial, 6,343 in each intervention phase.
- In order to determine the number of cases for a cluster-randomized study that correlates to the power of the number of cases determined by randomization at the individual level, this has to be multiplied with a design-effect factor: $DE=1 + (n-1)*p$. N is the number of individuals per cluster, and p is the intracluster correlation coefficient (ICC). The ICC is a measure for the similarity of the data of the cluster. It describes the similarity of cluster data by comparing the variance within clusters with the variance between clusters. According to the authors' knowledge, there is no study which describes inter- and intra-cluster variance in this setting. In various studies with dichotomous outcome, the design effect (DE) varies between 1.0 and 3.0³¹⁻³⁴.
- We assume a conservative design effect (DE) of 2.9. This results in a necessary number of cases of 36,788 patients, or 18,394 per study arm. With a DE of 2.9 in an individual randomization, 20 clusters and 635 patients per cluster, the corresponding ICC is 0.003. This assumed ICC is justified because we assume only a small variance between clusters.
- Assuming an average number of 30 beds per ward, an average length of stay of 10 days per patient and 90% bed occupancy, a single ward will treat 988 patients per year, 20 wards will treat 19,764 patients each year and 39,528 patients in total. Thus, 20 wards will be enrolled.

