Study population	
Inclusion criteria	
 • Adult medical and surgical Non-ICUs with approval from the medical director and head nurses, approximately 1000 admissions/year and an expected non-varying average length of stay for the 2 intervention periods • Ability to implement a universal ESBL-E admission and discharge screening • Written approval of the study from the local Institutional Review Board (IRB)
Exclusion criteria	
 • Transplant and paediatric wards, ICUs • Wards planning to enrol subjects in a study of an investigational agent administered for the purpose of eradicating or preventing colonization with ESBL-E or to reduce the likelihood of transmission of these bacteria
Sample Size	
Assuming an average new acquisition of ESBL-producers in hospital of 0.8/100 patients on non-ICUs, a design effect (DE) of 2.9 and a corresponding intracluster correlation coefficient (ICC) of 0.003, 20 wards with 36.788 included patients (18.394 per study arm) will have the a power of at least 80% to detect at least a 50% reduction in risk in wards during CI vs. SP period with a Type I error rate of 0.05 for a 2-sided test.

Randomization	
Randomization will occur at the ward level with a block size of 2. Groups of two consecutive wards will be randomized to one of the two arms.

Data Analyses	
For the primary efficacy analysis, incidence density of nosocomial ESBL-E acquisition will be computed at hospital level and ward level. A one degree of freedom test from an analysis of multivariate model will be used to test for differences in mean incidence density ratios of ESBL-E acquisition between the two strategies. This will be calculated by Poisson or negative-binomial regression analysis with monthly aggregated data using Generalized Estimating Equation (GEE) models with adjustment by several confounding parameters besides cluster effects by ward and hospital.

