Standard precautions (SP) may be as effective for limiting the spread of ESBL-E, especially when hand hygiene compliance is high¹⁷, and one study even found lower hand hygiene compliance under isolation conditions¹⁸.

Currently, many hospitals in Europe are unable to isolate patients with MDRO due to shortage of single rooms, while, the prevalence of intestinal ESBL-E-carriage among healthy people^{19, 20},²¹ and people admitted to the hospital^{22, 23} has risen sharply to 3-7 % depending on the setting and the population studied. Moreover, if ESBL-E-carriers are identified solely by cultures

obtained for clinical purposes, many asymptomatic patients colonized with ESBL-E will remain undetected and thus will not be cared for with contact precautions.

Hence, a combined approach of active surveillance screening at admission and CI of detected ESBL-E-carriers would be the logical consequence. However, this would increase the management costs for ESBL-E-patients even further.

Implementing HICPAC guideline recommendations would have considerable cost implications and impact on the quality of patient care²⁴. Therefore, adding contact precautions for the rapidly increasing number of patients colonized with ESBL-E should be based on solid evidence.

Last but not least, transmission prevention should not be considered an end in itself but rather one particular strategy to achieve the higher goal of reducing clinical infections and associated morbidity and mortality¹². This should also be investigated before final conclusions about isolation strategies for ESBL-E-patients are made.

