5.10. ENDPOINTS AND OUTCOMES

5.10.1. PRIMARY ENDPOINT

Incidence density of colonization with ESBL-E across the study periods.

- The primary outcome is the nosocomial ESBL-E-acquisition rate per 1,000 patient days. Acquisition of ESBL-E-carriage is defined as recovery of ESBL-E isolates from clinical and/or rectal screening specimens >3 days after hospital admission (admission day = day 1) from patients with negative admission screening results. If a patient is discharged from the ward and re-admitted to the ward on the same or the following day, then the discharge will be ignored in the primary analysis. If the readmission occurs later, the patient will be treated as a new case.

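### The stated design effect, ICC, patient number and power do not agree, because the ICC was matched to the cluster size before inflation and the crossover was left out

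*Protocol*

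**What the plan says.** Protocol section 9.1 builds the sample size in steps. The acquisition risk under standard precautions "is assumed to be at least 0.8 per 100 patients in Non-ICUs", and "the study is powered to detect a 50% reduction in the incidence of ESBL-E-acquisition compared to the SP strategy". This gives 6,343 patients per strategy, 12,686 in total, under individual randomization. That total is multiplied by an assumed design effect of 2.9 to reach 36,788 (18,394 per strategy). The design effect is then translated into an ICC: "With a DE of 2.9 in an individual randomization, 20 clusters and 635 patients per cluster, the corresponding ICC is 0.003". The section goes on to call 0.003 an assumed ICC and to defend it by the small variance expected between clusters.

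The only clustering formula given is DE = 1 + (n − 1) × ICC, with n defined as the individuals per cluster. Sections 5.1 and 5.3 have every ward apply both strategies for 12 months each.

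The synopsis, having named the design effect of 2.9 and the ICC of 0.003, states that "20 wards with 36.788 included patients (18.394 per study arm) will have the a power of at least 80" per cent, "with a Type I error rate of 0.05 for a 2-sided test". Section 9.1 closes by setting supply against this requirement: "20 wards will treat 19,764 patients each year and 39,528 patients in total". Section 5.10.1 counts an acquisition only "from patients with negative admission screening results", in a specimen taken more than 3 days after admission.

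**The concern.** The synopsis presents design effect, ICC, number of wards, number of patients and power as one consistent set. The ICC, however, was obtained at a cluster size that the trial will not have, and the formula behind it is for a parallel-group cluster trial. If the five figures cannot all hold, the power claim has no stated basis.

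This matters more than usual here. The primary hypothesis (section 4.2.1) is that contact isolation will not reduce acquisition, so a finding of no difference is the result the investigators expect. Readers will judge such a result by the power the protocol claims, and they need to be able to tell an informative null from an underpowered one.

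**Working it through.** **Inputs.** p1 = 0.008 and p2 = 0.004 (50% reduction), two-sided α 0.05, power 80%, 1:1 ratio, design effect 2.9, ICC 0.003, 20 wards with two periods each (section 9.1, synopsis, section 5.3). Section 9.1 labels the 0.80 as beta; it is read here as power.

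**Step 1: reproduce the plan.**
- Two-proportion formula: n = [1.96√(2 × 0.006 × 0.994) + 0.8416√(0.008 × 0.992 + 0.004 × 0.996)]² / 0.004² = 5,851 per strategy.
- With continuity correction: (5,851/4) × [1 + √(1 + 4/(5,851 × 0.004))]² = 6,341. The plan has 6,343.
- Inflation: 12,686 × 2.9 = 36,789. The plan has 36,788.
- ICC: 12,686/20 = 634.3, rounded up to 635, and (2.9 − 1)/(635 − 1) = 0.0030, as stated.

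The arithmetic is sound. What does not fit is the 635.

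**Step 2: use the planned cluster size.** 36,788/40 = 920 patients per ward-period (919.7).
- Design effect at ICC 0.003: 1 + 918.7 × 0.003 = 3.76.
- ICC that gives a design effect of 2.9: 1.9/918.7 = 0.0021.
- Effective size at 3.76: 18,394/3.756 = 4,897 per strategy.
- Power without continuity correction: z = (0.004 × √4,897 − 0.2141)/0.1092 = 0.60, so 73%.
- Power with the correction: n becomes (4,897 × 0.004 − 1)²/(4,897 × 0.004²) ≈ 4,410, z = 0.47, so 68%.

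Using all 39,528 patients (988 per ward-period) changes little: design effect 3.96, power 69.1% with the correction and 73.5% without.

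**Step 3: add the crossover.** For a cluster crossover, DE = 1 + (m − 1) × ICC − m × r × ICC, where m is the ward-period size and r is the between-period ICC divided by the within-period ICC. The protocol gives no r, so the values below are assumptions shown as a range (m = 919.7, ICC 0.003, 18,394 per strategy).

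| r | Design effect | Power, corrected | Power, uncorrected |
|---|---|---|---|
| 0 | 3.76 | 68% | 73% |
| 0.25 | 3.07 | 78% | 81% |
| 0.31 | 2.90 | 80% | 83% |
| 0.50 | 2.38 | 88% | 90% |
| 0.80 | 1.55 | 97% | 98% |

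Without the correction, 80% needs a design effect of at most 18,394/5,851 = 3.14, that is r = (3.756 − 3.144)/(919.7 × 0.003) = 0.22. With it, the limit is 2.90 and r = 0.31.

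**Step 4: patients available (conditional).** Supply is 30 × 366 × 0.9/10 = 988.2 per ward-year, and × 40 = 39,528. The surplus over 36,788 is 2,740, or 6.9% of the supply. Section 3 reports that carriage "has risen sharply to 3-7 % depending on the setting and the population studied", for healthy people and people admitted to hospital together. Removing 7% leaves 36,761, which is 27 below the requirement; removing 3% leaves 38,342, which is above it. This matters only if 0.8 per 100 is a risk per patient with a negative admission screen.

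**The case against.** The best defence is that the sample size does not rest on the ICC. The plan assumes a design effect of 2.9, near the top of a cited range of 1.0 to 3.0, multiplies by it, and only afterwards works out an ICC. Given 2.9, the 36,788 patients do yield 80%, and relabelling the ICC as 0.0021 would restore agreement. The protocol also says openly that no variance data exist for this setting. This stands as far as it goes: 36,788 follows from the assumed design effect. It does not remove the contradiction, because section 9.1 defends 0.003 as an assumption and the synopsis makes it a condition of the power claim.

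The second defence is that leaving out the crossover is conservative. That is correct, and it is why no shortfall can be claimed. The power figures also depend on the continuity correction, which the planned Poisson or negative-binomial GEE analysis does not use.

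A reader might infer more than the documents support:
- **That the trial is underpowered.** The between-period correlation is not given, and moderate values put power above 80%.
- **That the design effect should be 6.5.** Taking 1,839 patients per ward as the cluster gives 1 + 1,838.4 × 0.003 = 6.5 and power of 43% to 49%. This treats both periods of a ward as one cluster in a parallel trial, which this is not.
- **That the wards cannot supply enough patients.** Multiplying 12,686 by 3.76 and comparing with 39,528 holds the design effect fixed while the clusters grow, so it repeats the error at issue.
- **That short stays and missed swabs cut power much further.** The documents give neither a distribution of stay nor swab completeness, and if 0.8 per 100 is per admitted patient, such patients are already in the denominator.

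**Conclusion.** The point holds in a limited form. Design effect 2.9, ICC 0.003, 20 wards, 36,788 patients and at least 80% power cannot all be true on the plan's own formula. At the planned ward-period size, ICC 0.003 implies a design effect of 3.76 and power of about 68% to 73%, and a design effect of 2.9 implies an ICC of about 0.0021. This part needs no outside figure.

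The direction of the error in true power is not established. The missing crossover term could bring power to 80% or well beyond it, depending on a correlation the protocol does not state. The claimed power is unsupported, not shown to be too low.

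The count of available patients is a secondary point. Section 9.1 does not say whether 0.8 per 100 refers to admitted patients or to those with a negative admission screen. On the first reading there is no shortfall. On the second, the surplus is just used up at 7% carriage and is not at 3%.

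**What to change.** No extra enrolment and no change to design, endpoint or analysis is called for. Section 9.1 and the sample-size sentence of the synopsis should:
- use the cluster-crossover design effect, with the ward-period size in place of 635;
- state a within-period ICC and a between-period correlation, each with a range, and correct the ICC of 0.003 if the design effect of 2.9 is kept;
- say which patients form the denominator of 0.8 per 100, and count available patients on that same denominator;
- replace the claim of at least 80% power with the resulting range.

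The cost is a rewrite of one section and one synopsis sentence. The downside is that the stated power becomes a range that may include values below 80%.

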9.2. STATISTICAL PLAN

9.2.1. DESCRIPTIVE STATISTICS

Description of parameters will be done as figures and percentages for categorical parameters, as mean and standard deviation for normal-distributed continuous parameters and as median and interquartile range (25% percentile, 75% percentile) for nonnormal-distributed continuous parameters.

Depending on the distribution of the parameters, differences will be tested using Fisher's Exact test, Chi-square test, T-test or Wilcoxon rank-sum test. Differences in incidence densities will be tested by Chi-square test for incidence densities..

9.2.2. COMPARISON OF HOSPITAL AND WARD CHARACTERISTICS

Ward-level data will be compared between the two study arms.

9.2.3. ANALYSES OF PRIMARY OUTCOMES

The incidence density of ESBL-E-acquisitions in the SP strategy and the CI strategy will be compared in total and at study arm, hospital level and ward level.

In the univariate and multivariable analysis, crude and adjusted incidence-density ratios of ESBL-E-acquisition between the two strategies will be calculated by Poisson or negative-binomial regression analysis with, at best, weekly (if this is impossible at least monthly) aggregated data using Generalized Estimating Equation (GEE) models. Additionally, a Generalized Linear Mixed Model (GLMM) will be used to consider temporary trends in the periods. In total, 480 observation months will be analysed for the 20 wards with 12 observation months each per IC strategy. To analyse 1 degree of freedom in the regression model (e.g. a dichotomous parameter or a continuous parameter), 20 observations are required. The log number of patient days will be treated as offset parameter.

The models will take into account for the clustering effects "hospital" and "ward" and will consider the following parameters: strategy, type and size of ward, type and size of hospital, antibiotic use of different antibiotic groups (DDD/1000 patient days or PDD/100 patients), staff equipment and the burden of ESBL-E at admission (ESBL-E patients on admission per 100 admitted patients), after grouping wards into "higher" or "lower" ESBL-E burden based on median proportion of ESBL-E carriers on admission.

A GLMM model with parameters not on the causal pathway between exposure and outcome and based on expert knowledge and will be considered (i.e. strategy, antibiotic use, staff equipment, burden of ESBL-E on admission, time trend). Parameters with a causal connection

to nosocomial ESBL-E-acquisitions such as AHC and single room use will not be considered in this model.

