5.1. STUDY DESIGN

The study is a two-arm, cluster-randomized, controlled study (cRCT) of two IC strategies with cross-over design, which will be performed in 4 European countries to achieve high external validity of study results.

An attempt will be made to identify all intestinal ESBL-E-carriers by active surveillance testing and cultures obtained for clinical indications.

Two IC strategies (CI and SP) will be compared for ESBL-E-positive patients in different units for 12 months each. Because these IC strategies will be implemented as a unit-wide measure, all patients hospitalized in a specific unit will be subjected to the allocated IC strategy of the unit (figure 1). Wards will be assigned to the IC strategy in a random order and will then switch strategies after a wash-out period of one month in the following year.

Figure 1: Study design WP5

The two strategies are as follows:

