5.3. CONTACT ISOLATION (CI) (= INTERVENTION ARM)

All patients who are known to be colonized/infected with ESBL-E prior to admission or as a consequence of the surveillance cultures and/or of cultures obtained for clinical indications will be cared for using contact precautions, preferably in a single room or in a shared room with patients who are colonized with the same organism. If isolation in a single room or a shared room with patients colonized with the same organism is impossible, gloves and gowns/aprons will be used for all interactions with the patient or the patient's environment in a shared room. Clean gloves and gowns/aprons will be used for all interactions that involve direct contact with the patient or the patient's environment⁷. Non-sterile gloves are considered adequate; non-latex-gloves are used for medical staff and/or patients with latex allergy. Gloves should be changed after contact with infectious material, such as blood, stool, urine or wound drainage. Gloves should be removed immediately after use and hand hygiene should be practiced before touching non-contaminated surfaces or going to another patient. Clean gowns/aprons should be donned if contact with the patient or with environmental surfaces in the patient's room is expected. Gowns should be removed promptly after use and HH should be practiced before touching non-contaminated surfaces or going to another patient. HH will be performed according to WHO's "Five Moments"²⁵. As the intervention strategy will be implemented as a unit-wide IC measure, all patients known to be colonized/infected with ESBL-E-producing bacteria will be subjected to this IC strategy on wards in the CI phase of the trial.

Both strategies (SP and CI) will be applied in all units for a period of 12 months each with a washout period of one month between the 2 study periods.

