5.9. RANDOMIZATION

Randomization will occur at the ward level. Groups of two consecutive wards will be randomized to one of the two arms.

The investigators will be aware of the assigned IC strategy in order to monitor implementation of each strategy. Data analysts will be unaware of the IC strategy assignment.

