9.2.4. ANALYSES OF SECONDARY OUTCOMES

The incidence density of hospital-acquired infections caused by ESBL-E in the CI period with the SP period will be compared in total and ward levels. Additionally, a regression model will be performed to adjust by confounders.

The incidence density of clinical isolates with ESBL-E will be analysed by segmented regression using 31 observation months (3 month baseline, 12 month first intervention, 1 month washing out, 12 month second intervention, 3 month post intervention). Incidences of the different study phases will also be compared and tested.

To analyse the difference in HH practice for known ESBL-E patients in the two intervention periods, AHC will be calculated for ESBL-E-positive patient days (per ESBL-E-positive patient day) in both intervention periods at total and ward levels and differences will be tested.

To analyse the differences in the HH practice between known ESBL-E-carriers (use in ESBL-E-positive patient days) and patients not known to be ESBL-E-carriers (use in ESBL-E-negative patient days), AHC consumption in ESBL-E-positive and -negative patient days will be calculated separately at total and ward levels and by intervention period and differences will be tested.

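### Comparing CI with SP within one sequence or one ward cannot separate strategy from year; such results should carry no p-values, and the pooled GEE needs a period term

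*Protocol*

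**What the plan says.** **Design.** Section 5.1: "Wards will be assigned to the IC strategy in a random order and will then switch strategies". Section 5.3: "Both strategies (SP and CI) will be applied in all units for a period of 12 months each", with a one-month washout between. Section 5.9: "Groups of two consecutive wards will be randomized to one of the two arms". Randomisation therefore fixes only which strategy comes first. The schedule in section 5.7 adds up to 3 + 12 + 1 + 12 + 3 = 31 months, the same length as the window of 08/2013 to 02/2016 in section 5.8. On that schedule all wards share the same two intervention years.

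**Primary outcome.** Section 9.2.3 says that incidence densities under the two strategies "will be compared in total and at study arm, hospital level and ward level". It then describes crude and adjusted ratios from pooled Poisson or negative-binomial GEE models over 480 ward-months. The listed parameters are strategy, ward and hospital type and size, antibiotic use, staffing and ESBL-E burden at admission. Time enters separately: "Additionally, a Generalized Linear Mixed Model (GLMM) will be used to consider temporary trends in the periods".

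**Infections.** Section 9.2.4 says that the incidence density "in the CI period with the SP period will be compared in total and ward levels".

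**Test.** Section 9.2.1: "Differences in incidence densities will be tested by Chi-square test for incidence densities". No adjustment for time is attached to this test, and neither 9.2.3 nor 9.2.4 labels the sequence- or ward-level results as descriptive.

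**The concern.** In a two-period crossover with one switch per ward, the randomised contrast lies between the two sequences. Inside one sequence, or one ward, strategy and calendar year are the same variable. No covariate or period term can separate them there, because the concurrent comparator is in the other sequence.

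The Background (section 3) describes ESBL-E prevalence in Europe as rapidly increasing and carriage on admission as having risen sharply, so a change between the two years is plausible. A shared rise would make CI look harmful in wards that go from SP to CI and protective in wards that go from CI to SP. Someone reading separate ratios and p-values by sequence or ward could take this for a strategy effect that differs between groups of wards. The risk is over-interpretation of subsidiary results. The pooled estimate is a different matter and is treated below.

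**Working it through.** **1. Inputs from the protocol.**
- Acquisition risk 0.8 per 100 patients, 50% reduction, 6,343 patients per phase before the design effect, 988 patients per ward-year, 20 wards (section 9.1).
- Two-sided alpha 0.05, power 80% (Synopsis, Sample Size).
- Block size 2 (Synopsis, Randomization).

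The plan's figures reproduce. Two proportions, 0.8% versus 0.4%, with continuity correction give 6,341 per phase (stated: 6,343). Patients per ward-year: 30 × 0.9 × 366 / 10 = 988.

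**2. Assumptions not in the protocol.** Ten wards per sequence; equal patient-days in both years; Poisson counts without overdispersion; a year-2/year-1 ratio R common to all wards, varied over a range.

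**3. Expected events per year.** One ward: 988 × 0.008 = 7.9. One sequence: 10 × 7.9 = 79.

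**4. Aliasing.** With no strategy effect, the expected CI/SP ratio is R in the SP-then-CI sequence and 1/R in the CI-then-SP sequence. R = 1.2 gives 1.20 and 0.83; R = 1.5 gives 1.50 and 0.67.

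**5. False-positive rate of the chi-square.** The statistic is (a − b)² / (a + b) on the two yearly counts, rejecting above 3.84. For one sequence at R = 1.2, the standardised shift is 79 × 0.2 / √(79 × 2.2) = 15.8 / 13.2 = 1.20, which gives about 22%. Poisson simulation agrees:

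| R | Within one sequence | Within one ward |
|---|---|---|
| 1.0 | 5% | 4.8% |
| 1.1 | 9% | 5.4% |
| 1.2 | 22% | 6.6% |
| 1.3 | 42% | 8.6% |
| 1.5 | 80% | 14.6% |

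A falling rate acts the same way: within one sequence, R = 0.8 gives 26% and R = 0.7 gives 53%.

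**6. Ward level.** With 7.9 events against 3.95 (a halving), simulated power is about 19%. Twenty independent tests at 5% give 1 − 0.95²⁰ = 0.64 for at least one false positive with no drift at all. The simulated single-test rate of 4.8% gives 0.63.

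**7. Pooled comparison.** With k wards going from SP to CI, the expected CI/SP ratio is (kR + 20 − k) / (k + (20 − k)R).
- k = 10: the ratio is 1.00 for every R, and simulated error stays at 5%.
- k = 12: R = 1.2 gives 22.4 / 21.6 = 1.04; R = 1.5 gives 26 / 24 = 1.08.

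Shared drift therefore cancels under balance and leaves a small bias under imbalance if no period term is fitted.

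**8. Room for a period term.** Section 9.2.3 asks for 20 observations per degree of freedom and counts 480 ward-months: 480 / 20 = 24 degrees of freedom. A period term uses one.

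**The case against.** Several counter-arguments have force.

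- *Ward level* may mean only that rates are computed per ward. The Synopsis says that primary analyses are at ward level and then names a single one-degree-of-freedom test. No section announces 20 separate p-values for acquisition. This stands: the ward-level figures describe what would follow if such tests were run.
- *Study arm* often means strategy in this document. Sections 5.2 and 5.3 label SP and CI as the arms, and section 9.1 gives patients per study arm. If it means that in 9.2.3, the phrase is merely redundant. However, a comparison of SP with CI at the level of the arm makes sense only if arm means sequence, which section 5.9 permits. The term needs defining.
- The primary-outcome and infection sentences say compared, not tested. The link to a test is a general line under descriptive statistics. This also stands, although that line covers differences in incidence densities without exception, and 9.2.4 does call for tests at ward level for handrub consumption.
- The drift is assumed. The Background speaks of carriage prevalence, not of yearly change in ward acquisition. At R = 1.1 the within-sequence error is only 9%.

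A reader might infer that calendar change is credited to the strategy in the primary result and that the trial makes no randomised comparison. The protocol does not support that. The total comparison and the GEE and GLMM use both sequences, shared drift cancels when these are balanced, and the GLMM carries a time trend. Hospital-level comparison is not necessarily aliased either, since a hospital with four wards can hold both orders, although the protocol does not say that blocks fall within hospitals.

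**Conclusion.** The concern holds in limited form. A CI–SP contrast within one ward, or within one sequence if that is the meaning of *study arm*, is a before-and-after contrast and cannot identify the strategy effect. Tested by the stated chi-square within a sequence, it would reject in about 9% to 80% for R between 1.1 and 1.5 with no strategy effect. These rates rest on the assumed R, the 10:10 split and Poisson variation; overdispersion would raise them. At ward level, drift is a minor contributor, and low power and multiplicity are the reasons not to test.

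The primary inference remains randomised. Its one weakness here is that the listed GEE parameters have no period or time term, which matters if the sequences end up unequal in wards or patient-days. Section 5.8 allows wards to be withdrawn or replaced, so exact balance is not assured. This should be corrected, but it does not undermine the trial.

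**What to change.** 1. Section 9.2.3: define *study arm*, and use separate words for strategy and for randomised sequence.
2. Section 9.2.3: state that inference on CI versus SP rests on the pooled model over both sequences, and add a period (calendar-time) term to the GEE as well as the GLMM.
3. Section 9.2.3: report acquisitions and patient-days by sequence, period and ward descriptively, without p-values. Keep the computation of ward-level rates so that the section stays consistent with the Synopsis. Showing both sequences is useful, because opposite ratios reveal a period effect.
4. Section 9.2.4: make the same change to the ward-level CI–SP comparison of infections, and to the ward-level CI–SP comparison of handrub use. Comparisons of known carriers with other patients inside one period do not have this aliasing.
5. Keep hospital-level ratios only for hospitals with wards in both sequences. If variation in effect is of interest, estimate one ward- or hospital-by-strategy variance component in the pooled model.

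The cost is wording, one degree of freedom, and the loss of per-sequence and per-ward p-values. Data collection and sample size do not change.
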